#### A summary of the HVPG procedure is as follows [R20-3977]:

Under local anaesthesia and ultrasound guidance, a catheter introducer sheath is placed in the right internal jugular vein. Using fluoroscopic guidance, a balloon catheter is advanced into the inferior vena cava (IVC) and inserted into a large hepatic vein. Correct and sufficient wedge position of the catheter is ensured by injecting contrast media while the balloon is blocking the outflow of the cannulated hepatic vein. After calibrating the external pressure

Boehringer Ingelh	eim	29-Nov 2023
BI Trial No.: 1366	-0055	
c42374778-02	Clinical Trial Protocol	Page 55 of 98

transducer, continuous pressure recordings are obtained with triplicate recordings of the WHVP and FHVP. The difference between FHVP and WHVP is referred to as HVPG, with values  $\geq 10$  mmHg indicating CSPH. Before removing the catheter, pressure readings obtained in the IVC at the same level, as well as the right atrial pressure, are recorded.

BI-VQD-12177\_40-106\_AD-03 (22.0)

Page 56 of 98

Proprietary confidential information © 2023 Boehringer Ingelheim International GmbH or one or more of its affiliated companies

#### 5.2.1 Physical examination

A complete physical examination must be performed at the two time points specified in the Flow Chart; further physical examinations are only required if the trial participant reports symptoms. A complete physical examination includes, as a minimum, general appearance, neck, lungs, cardiovascular system, abdomen, extremities and skin.

5.2.1.1 Anthropometric measurements (height, weight, waist and hip circumference)

Measurement of height, body weight, waist and hip circumference will be performed at the time points specified in the Flow Chart. Height will be measured at Visit 1a only. The results of anthropometric measurements must be included in the source documents available at the site.

Whenever possible, weight measurements should always be performed on the same weighing scales for one trial participant. In order to get comparable body weight values, the assessment should be performed in the following way:

- shoes, coat / jackets and any headgear should be taken off
- pockets should be emptied of heavy objects (i.e. keys, coins etc)
- after bladder voiding

The measuring tape used for waist and hip circumference should be made of a material that is not easily stretched, such as fiberglass. Waist circumference measurements should be made around a trial participant's bare midriff, after the trial participant exhales while standing without shoes and with both feet touching and arms hanging freely. Waist circumference should be determined by measuring the midpoint between the lowest rib and the iliac crest. The tape should be placed perpendicular to the long axis of the body and horizontal to the floor and applied with sufficient tension to conform to the measurement surface.

Hip circumference measurements should start at one hip, wrapping the measuring tape around the widest part of the buttocks, and around the other hip to the front. Coats / jackets should be taken off and pockets emptied to ensure a close measurement and with both feet touching and arms hanging freely.

#### 5.2.2 Vital signs / home blood pressure and heart rate monitoring

Vital signs (SBP, DBP, as well as HR [pulse rate]) will be evaluated at trial visits at the time points specified in the Flow Chart, prior to blood sampling and prior to the 12-lead ECG. BP measurements should be recorded in the eCRF to the nearest 1 mmHg. BP measurements should be performed on the non-dominant arm. HR should be measured electronically or by palpation, and counted for one minute. BP and HR measurements should be taken after trial participants have rested quietly, in the seated / supine position, for at least 5 minutes. The measurements recorded at the trial visit must be included in the source documents available at the site.

At screening (Visit 1a), the site should use their preferred method to measure vital signs. From Visit 2 onwards, vital signs should be measured using the trial participants home BP monitoring equipment (refer to Section 5.2.2.1) in order to have a consistent method for the duration of the trial. This includes the pre- and post-dose vital signs measurements during the dose-titration period and at the subsequent visit (refer to the Flow Chart and Section 6.2).

#### 5.2.2.1 Home blood pressure and heart rate monitoring

Home BP and HR monitoring will be performed by the trial participant as specified in the Flow Chart. Electronic BP and HR monitoring equipment will be provided for this purpose. Site staff will train the trial participant in the correct use of the equipment at Visit 2, explaining that it must be used only to record BP and HR measurements belonging to the trial participant. Subsequent refresher training should be provided at subsequent visits if required.

Trial participants will be asked to measure their BP and HR every day in the morning, soon after waking up prior to much physical activity, and after resting seated for approximately 5 minutes. Measurements must be taken before administration of the morning dose of trial medication. The electronic readings will be stored in the memory of the home BP and HR monitoring equipment.

If, at any time after trial medication intake, a trial participant experiences symptoms suggestive of hypotension (e.g. he / she feels light-headed / dizzy, sees black spots, suffers from weakness etc.), particularly if the symptoms occur whilst standing up, or if he / she has any other symptoms in between trial visits, additional BP and HR reading(s) can be taken and the trial participant should report these symptoms at the next trial visit. The trial participant should bring the home BP and HR monitoring equipment with them to each trial visit (refer to the Flow Chart) for the site staff to review the electronic readings, and to use for the measurement of BP and HR during trial visits from Visit 2 onwards (refer to Section 5.2.2). Any BP / HR measurements which, following review, are evaluated as AEs, must be included in the source documents available at the site (refer to Section 8.3.1).

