have been chosen as part of the screening procedures to further investigate the trial participants' status, to establish baseline values for comparison with treatment, and to gain further insight into the use of non-invasive methods to investigate liver function and portal pressure. These assessments will be repeated (refer to Figure 3.1: 1 and the Flow Chart) to assess a time-dependency of the treatment.

Following randomisation, the trial design includes a dose-titration period. The mechanism related vasodilatation of BI 685509 can lead to orthostatic dysregulation and hypotensive episodes (refer to Table 1.4.2: 1). The orthostatic dysregulation is dose-limiting and clinical tolerability is improved if the dose is titrated. A BID administration also allows the total daily exposure of BI 685509 to be further increased while high peak concentrations are avoided. Hence, in this trial, a dose-titration regimen of BID to BID to BID to BID will be followed.

Trial participants selected for this trial have a risk for further decompensation. A DMC, independent from the Sponsor, will therefore be established to review safety data at intervals to identify any potential risks and / or the need for implementation of further safety measures. The tasks and responsibilities of the DMC members will be detailed in the DMC charter (refer to Section 8.7).

An independent AC will also be established for adjudication of hepatic injury. The tasks and responsibilities of the AC members will be detailed in the AC charter (refer to Section 8.7).

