## 4.1.4 Drug assignment and administration of doses for each trial participant

Trial medication will be dispensed at the investigational sites in accordance with the Flow Chart. At dispensing visits trial participants will be given the appropriate number of medication kits for BI 685509 (range 1-2) depending on the interval between the visits (for further kit details refer to Section 4.1.6). The last dose of BI 685509 will be administered in the evening of the day before the EoT visit.

All trial participants, regardless of the treatment group they are assigned to, will start at Visit 2 on a dose of BI 685509 BID or matching placebo. At Visit 3, 7 days later, and again at Visit 4, a further 7 days after Visit 3, all trial participants will be up-titrated first to a dose of BI 685509 BID or matching placebo, and then to a dose of BI 685509 BID or matching placebo. In this way the blind across treatment groups will be maintained (refer to Table 4.1.4: 1). Trial participants will be informed about the dose titration period and will be made aware that up-titration for BI 685509 is being used. If a trial participant does not tolerate an up-titration, e.g. due to orthostatic dysregulation, the rules in Section 4.1.4.1 must be followed. From Visit 4 onwards, trial participants will continue to receive the maximum dose of 3mg BI 685509 BID (unless a down-titration is required), until reaching the EoT visit 8 weeks after starting the trial medication.

If a trial participant has an AE that, based on Investigator judgement, may be related to BI 685509, the trial medication can either be:

• interrupted (i.e. the trial medication is stopped, and subsequently re-started. The uptitration approach described above is followed.)

OR

• the dose can be reduced (down-titrated) for BI 685509 if the trial participant has successfully completed the dose titration period (i.e. Visit 4).

For further details refer to Sections 4.1.4.1 and 4.1.4.2.

All trial medication assignments, including up / down-titrations for BI 685509 and provision of replacement kits, will be managed through the IRT system. Down-titrations of BI 685509 must not be performed by instructing the trial participant to take less than the two daily doses (refer to Section 4.1.4.1).

Page 46 of 98

Proprietary confidential information © 2023 Boehringer Ingelheim International GmbH or one or more of its affiliated companies

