#### 4.1.4.1 Rules for down-titration in case of intolerance to BI 685509

If a trial participant has an AE that, based on Investigator judgement, may be related to trial medication, the down-titration rules below must be followed. These rules apply if the trial participant has successfully completed the dose titration period (i.e. Visit 4) and is either still taking their final assigned dose of trial medication, or if they have missed  $\leq 3$  consecutive doses. If the trial participant has not successfully completed the dose titration period (i.e. Visit 4), down-titration is not permitted; in case of persistent AEs or severe effects, the trial participant must permanently discontinue treatment (refer to Section 3.3.4.1).

• if the trial participant is receiving BID BI 685509 the dose will be down-titrated one level to 2 mg BID BI 685509

Once down-titration has taken place, no further up-titration will be permitted. If a trial participant continues to have an AE, or a new AE develops, that based on Investigator judgement, may be related to trial medication, a second down-titration will be permitted:

• if the trial participant is receiving BID BI 685509 the dose will be down-titrated to BID BI 685509

Down-titration must not be performed by taking less than the two daily doses or by splitting tablets so that a whole tablet is not taken. Down-titration will be managed through the IRT system (refer to Section 4.1.4). After the successful completion of the dose titration period (i.e. Visit 4), in case of persistent AEs despite down-titration, or severe effects at any dose, permanent treatment discontinuation should be considered (refer to Section 3.3.4.1). Trial participants who are down-titrated will need to return to the investigational site to receive their continuing supply of trial medication, either at the next scheduled visit or via an unscheduled visit.

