#### 5.2.6.1.4 Adverse events of special interest

The term adverse events of special interest (AESI) relates to any specific AE that has been identified at the project level as being of particular concern for prospective safety monitoring and safety assessment within this trial, e.g. the potential for AEs based on knowledge from other compounds in the same class. AESIs need to be reported to the Sponsor's Pharmacovigilance Department within the same timeframe that applies to SAEs; please see Section 5.2.6.2.2.

The following are considered as AESIs:

• Hepatic injury

A hepatic injury is defined by alterations of the hepatic laboratory and clinical parameters after randomisation as detailed by the removal and stopping criteria in Section 3.3.4.1 and Appendix 10.2

These laboratory findings constitute a hepatic injury alert and patients showing these abnormalities need to be followed up according to the "DILI checklist" which can be downloaded from the eDC system. In case of clinical symptoms of hepatic injury (e.g. encephalopathy, nausea, vomiting, pruritus, severe fatigue, icterus, etc.) without laboratory results (ALT, AST, total bilirubin, INR) available, the Investigator should make sure these parameters are analysed, if necessary in an unscheduled blood test. Should the results meet the criteria of the hepatic injury alert, the procedures described in the DILI checklist should be followed.

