#### 6.1 VISIT SCHEDULE

All visits should be scheduled according to the Flow Chart. Each visit date (with its permitted time window) should be calculated in relation to the day of randomization (i.e. Day 1). During the dose titration period of the trial (i.e. from Visit 2 to Visit 4), scheduled trial visits must be at least 7 days apart, since a trial participant must have taken the preceding dose of BI 685509 for at least 7 consecutive days before up-titration occurs (refer to Section 4.1.4). For this reason, if the permitted time window (+2 days) is applied to Visit 3, the permitted time window must also be applied to Visit 4 (+2 days). Missed visits should be rescheduled as soon as possible ideally within the permitted time window for that visit. If any visit has to be rescheduled, subsequent visits should follow the original visit schedule. Unscheduled visits can be performed at the discretion of the Investigator at any time for safety reasons or, for instance, to provide trial medication (e.g. a re-start of BI 685509 following treatment interruption).

All visits will take place at the investigational site, and ideally they should be performed in the morning. In the randomised treatment period, on the morning of a visit, the trial medication will be administered as part of the visit. Therefore, on these days, trial participants should be instructed not to take their morning dose in advance of their clinic visit (refer to Section 4.1.4).

The fasting status of a trial participant should be in accordance with the Flow Chart and will be recorded in the eCRF. Trial participants who fail to follow the afore-mentioned instructions should have the visit re-scheduled as soon as possible, ideally on the following day.

In the event of force majeure or other disrupting circumstances (refer to Section 6), physical trial participant visits to the sites may not be feasible or may need to be restricted to ensure trial participant safety. Based on a thorough assessment of the benefits and risks, the following visit may be performed at the trial participant's home, remotely (by phone) or as a combination of home and remote visit:

• Visit 6

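### Protocol 5.2.2.1 asks participants with symptoms of low blood pressure at home to report them at the next visit, so the site may not learn of them for 7 to 9 days in titration and 14 to 22 days on maintenance

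*Protocol*

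**What the plan says.** Protocol Section 5.2.2.1 has participants measure BP and HR once each morning, seated, before the first dose of the day. The device stores the readings, and staff look at them when the participant brings it to a visit.

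The section then covers a participant who feels light-headed, sees black spots or is weak at any time after taking trial medication, "or if he / she has any other symptoms in between trial visits". For all of these, "additional BP and HR reading(s) can be taken and the trial participant should report these symptoms at the next trial visit".

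Other sections bear on what the site could do once it knows:

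- Section 3.2, on the main tolerability problem: "The orthostatic dysregulation is dose-limiting and clinical tolerability is improved if the dose is titrated".
- Section 4.1.4: "If a trial participant has an AE that, based on Investigator judgement, may be related to BI 685509, the trial medication can either be" interrupted or, once titration has been completed at Visit 4, reduced.
- Section 4.1.4.1: "Trial participants who are down-titrated will need to return to the investigational site to receive their continuing supply of trial medication", at a scheduled or an unscheduled visit. Before Visit 4 is completed, down-titration is not allowed, and persistent AEs or severe effects mean permanent discontinuation.
- Section 6.1: "Unscheduled visits can be performed at the discretion of the Investigator at any time for safety reasons".

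**The concern.** The sentence sets a rule. An extra reading is optional (*can*), and the only thing the participant *should* do is wait for the next visit to report. Every protective step listed above depends on the investigator's judgement, so it cannot start until the investigator knows. The same holds for three other provisions: mandatory discontinuation for a related Grade 3 AE, the enrolment pause for repeated Grade 3 events (both Section 3.3.4.1), and the 24-hour reporting duty, which runs from awareness (Section 5.2.6.2.2).

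The symptoms in question are those of the effect that limits the dose. Grade 3 or higher hypotension or syncope, and discontinuation for either, are secondary endpoints (Section 2.1.3). At stake is how soon a symptomatic participant at home can be assessed, not any efficacy estimate.

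**Working it through.** **Inputs.** Planned days and windows come from the Protocol Flow Chart, with Section 6.1 and SAP Table 6.7:2 as cross-checks: Visit 2 Day 1; Visit 3 Day 8 (+2); Visit 4 Day 15 (+2); Visit 5 Day 29 (+2); Visit 6 Day 43 (±3, Days 40 to 46); EoT Day 57 (±5, Days 52 to 62). Titration visits must be at least 7 days apart (Section 6.1). Visit dates count from Day 1, so lateness at one visit does not shift the next. Dosing is twice daily.

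**Planned gaps.** 8−1 = 7; 15−8 = 7; 29−15 = 14; 43−29 = 14; 57−43 = 14. The sum is 56 days, which matches the 8-week treatment period.

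**Longest permitted gap** = latest day of the next visit minus earliest day of the current one. Scheduled doses = 2 × days.

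| Interval | Planned days | Longest with windows | Doses, planned / longest |
|---|---|---|---|
| Visit 2 to 3 (titration) | 7 | 10−1 = 9 | 14 / 18 |
| Visit 3 to 4 (titration) | 7 | 17−8 = 9 | 14 / 18 |
| Visit 4 to 5 | 14 | 31−15 = 16 | 28 / 32 |
| Visit 5 to 6 | 14 | 46−29 = 17 | 28 / 34 |
| Visit 6 to EoT | 14 | 62−40 = 22 | 28 / 44 |

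Each figure is the wait for a symptom that starts just after a visit. Later onset shortens it. Windows can also shorten the maintenance gaps, to 12, 9 and 6 days. Section 4.1.6 says that kits cover the visit windows, so supply would not end dosing earlier.

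**Does other monitoring close the gap?**

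1. *Daily home readings.* They precede the morning dose. Section 1.2.1 puts peak concentration at 0.5 to 1.0 hour after dosing in healthy volunteers and ties Cmax closely to orthostatic dysregulation. A seated pre-dose reading misses that period, and no transmission or alert is described.
2. *Clinic readings at 1 and 2 hours post-dose* (Flow Chart footnote 21). These cover visit days during titration and the subsequent visit, so they catch the first dose at each level but not the doses at home. Steady state takes about 3 to 5 days (Section 1.2.1). After the Day 15 up-titration that is about Day 18 to 20, which is 9 to 11 days before Visit 5.
3. *Up-titration only if the dose is tolerated* (Section 3.1). This is decided at visits, so it does not bring reporting forward.

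At home, then, symptoms and optional extra readings are the main post-dose signal, and the sentence directs the symptoms to the next visit.

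**The case against.** The strongest reply is that much participant-facing text is not public. The Flow Chart lists a reminder card whose footnote is not visible, Section 5.6 is a bare heading, and the consent pages were removed. A prompt-contact instruction could well be there. This stands as a limit: one cannot conclude that the trial lacks such an instruction. It does not cure Section 5.2.2.1, which would then say something different and need aligning.

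The risk is also managed in other ways. Participants with SBP below 100 mmHg, DBP below 70 mmHg or relevant orthostatic history are excluded. In the earlier hepatic-impairment trial all AEs were mild or moderate, and orthostatic intolerance resolved on continued treatment (Section 1.2.3). That trial had 49 patients treated for up to 4 weeks, so it tempers the point without removing it.

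Some stronger readings are tempting but not supported:

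- *That a symptomatic participant must keep taking the drug.* The sentence concerns readings and reporting. Section 3.3.4.1 lets participants stop when they wish, and Section 4.1.4.2 anticipates doses missed because of an AE.
- *That symptoms of hepatic injury are deferred too.* The wording about other symptoms is broad, but it sits in a home-BP section. Section 5.2.6.1.4 deals with hepatic symptoms separately: "the Investigator should make sure these parameters are analysed, if necessary in an unscheduled blood test".
- *That an average delay can be given.* It would need a distribution of symptom onset, which the documents do not supply. Uniform onset would be a guess, and the result would describe visit spacing rather than harm.

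**Conclusion.** The point holds as a cheap improvement to a safety instruction, with medium confidence. Read literally, Section 5.2.2.1 allows a wait of up to 7 planned days (9 with windows) in each scheduled titration interval. On maintenance it allows up to 14 planned days, or 16, 17 and 22 days with windows. The 22-day gap holds about 44 scheduled doses if dosing continues, so a reader should not take 14 days or 28 doses as the maximum.

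These are upper limits and not predictions. They assume that the participant follows the sentence exactly, that symptoms start just after a visit, and that no visit is missed. They also assume titration runs on schedule: one re-started after more than 3 missed doses (Section 4.1.4.2) can fall within a longer interval. A reader might infer that contact before the visit is forbidden, but nothing in the text bars it, and severe events would probably surface sooner.

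**What to change.** In Section 5.2.2.1, replace the clause on optional readings and next-visit reporting with: *the trial participant should take an additional BP/HR reading and contact the site promptly; symptoms and readings are also reviewed at the next visit.* The sponsor's medical team sets the timing and the symptom and BP thresholds. Align the reminder card and participant information. No dose, titration or stopping rule changes.

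The cost is one sentence in an amendment, matching participant material and a line in the home-BP training already held at Visit 2. Expect some extra calls and unscheduled visits, which Section 6.1 allows. There may also be more down-titrations, which are final ("Once down-titration has taken place, no further up-titration will be permitted"), and more interruptions, which restart titration after more than 3 consecutive missed doses. Sensible thresholds should limit both.

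SAP Section 4 records that the programme was stopped in May 2024 and that all subjects were to be discontinued early. The change is therefore for the protocol as written and for any later protocol that reuses the sentence.
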